6.6 Pharmacokinetic, Pharmacodynamic, Pharmacogenomic, and Other Biomarker Analyses

6.6.1 Pharmacokinetic Analyses

Analyses will be based on the pharmacokinetic analysis set.

The PK Analysis Set will be defined as:

The PK Analysis Set includes subjects from whom at least one quantifiable concentration of E7777 was observed at 9 µg/kg/day dose (both Main Study and Lead-In).

Serial PK assessment of E7777 will be performed on all subjects in the Lead-In and on the first 12 subjects in the Main Study, using serial blood PK sampling on Day 1 in Cycles 1, 3, and 5, with sparse sampling in Cycle 8. In addition, sparse sampling will be performed in the rest of the subjects on Day 1 of Cycle 1.

The PK analysis will be done using PK Analysis Set.

Serum concentration data for E7777 will be analyzed and summarized using descriptive statistics (n, mean, standard deviation (SD), median, minimum and maximum) by time point.

PK parameters will be derived for subjects with serial blood PK sampling using non-compartmental methods for E7777 on Day 1 of Cycles 1, 3 and 5. These include as data permit:

- Time to maximum concentration (t_{max})
- Maximum concentration (C_{max})
- Area under the curve from 0 to t ($AUC_{(0-t)}$)
- Area under the curve from 0 to infinity ($AUC_{(0-inf)}$)
- Elimination half-life ($t_{1/2}$)
- Total body clearance (CL)
- Volume of distribution at steady state (Vd_{ss})

Descriptive statistics (n, mean, standard deviation (SD), median, minimum and maximum, geometric mean (%CV)) will be used to summarize PK parameters. Geometric mean (%CV) will not be computed for t_{max} .

When presenting individual/raw values and summary statistics, the following rule will be applied: for drug concentrations and concentration-dependent pharmacokinetic parameters, all summary statistics (mean, standard deviation (SD), median, minimum and maximum, geometric mean) will have 3 significant digits. For t_{max} , raw values and median have fixed 2 decimal places.

The following figures will be prepared:

- Linear and semi-log plots of individual E7777 serum concentration versus time at each cycle and day for subjects with serial blood PK sampling
- Linear and semi-log plots of mean and SD for E7777 serum concentration versus time by cycle and day for subjects with serial blood PK sampling
- Box plot of pharmacokinetic parameters (C_{max} , $AUC_{(0-t)}$, and $AUC_{(0-inf)}$) by cycle for subjects with serial blood PK sampling
- Relationship of Drug Exposure on Cycles (C_{max} , $AUC_{(0-t)}$, $AUC_{(0-inf)}$) (AbImpact = 0 Only) if applicable

Based on the immunogenicity (antibody positive, negative, etc.) additional PK analyses may be prepared.

Serum concentration data from the sparse PK sampling time points and the intense PK sampling time points from both lead-in and main phase will be analyzed using a population PK approach incorporating data from all studies of the E7777 program. The relationship of E7777 exposure and key efficacy and safety endpoints will also be assessed (as part of population PK/PD analyses). Details concerning the objectives and methods of these exploratory analyses will not be described in this SAP but will be described in a separate population analysis plan (PAP) authored by Modeling and Simulation of Clinical Pharmacology Science (M&S, CPhS), Medicine Development Center (MDC)-Eisai.

6.6.2 Immunogenicity Analysis

Analyses will be based on the safety analysis set.

Immunogenicity (formation of antibodies to E7777 or IL-2, and of neutralizing antibodies) will be assessed in all subjects in both the Lead-In and the Main Study. Immunogenicity assessment in serum will be performed using validated bioanalytical methods to screen, confirm, and characterize the presence of anti-E7777, anti-IL-2, and neutralizing antibodies. Only samples with confirmed positive antibodies to E7777 and/or IL-2 will be tested by a neutralizing antibody assay. A predose blood sample for immunogenicity assessment will be collected prior to dosing on Day 1 in Cycles 1, 2, 3, 5, and 8. After that, all subjects will be followed up for immunogenicity testing for anti-IL-2 on a 6-month schedule for 1 year and every year thereafter until antibody titers decrease to Baseline level or until study conclusion/termination. Blood samples will be collected prior to study drug administration.

Anti-E7777/IL-2 antibodies results (negative/positive) will be summarized by number of subjects and percentage by visit. For subjects with positive anti-E7777/IL-2 antibodies, the titer levels will be summarized using descriptive statistics (n, mean (SD), Q1, Q3, median, minimum and maximum) by visit. In addition, neutralizing anti-E7777/IL-2 antibodies results (negative/positive) will be summarized by visit.

The following figures will be prepared:

- Semi-log box plot of Anti-E7777 and Anti-IL-2 titers by cycle

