### 7.3 Clinical Experience With ONTAK and E7777

#### 7.3.1 Clinical Experience with ONTAK (Denileukin Diftitox)

Since E7777 and ONTAK have a common active moiety, clinical experience with ONTAK in T-cell lymphoma provides relevant background information. The most extensive clinical experience for denileukin diftitox is in CTCL. More than 300 subjects have been treated in Phase 3 and Phase 4 studies, including one randomized placebo-controlled trial. Data on efficacy, safety, pharmacokinetics (PK), and immunogenicity are summarized below:

- Efficacy: ONTAK has shown clinical efficacy at doses of 9 or 18 µg/kg/day administered intravenously for 5 consecutive days every 3 weeks, with an objective response rate (ORR) of 38% in 263 subjects.
- Safety: ONTAK is generally well tolerated, with the most notable AEs being infusion reaction and capillary leak syndrome (CLS). Please refer to the Investigator's Brochure (IB) for details on the safety profile.
- PK: After the first dose, ONTAK is rapidly distributed and has a terminal elimination half-life ( $t_{1/2}$ ) of 70 to 80 minutes. No accumulation was apparent between Day 1 and Day 5 of dosing, and the clearance increased from Cycle 1 to Cycle 3 corresponding to a 75% decrease in exposure.
- Immunogenicity: Immune response to ONTAK was tested in the Phase 3 studies. At baseline, 66% of subjects (N=95) tested positive for antibodies to denileukin diftitox; after 1, 2, or 3 cycles of treatment, 94%, 99%, and 100% of subjects tested positive, respectively. Antibody titers increased after 2 cycles, with PK parameters indicating decreased systemic exposure to drug.

Please refer to the Investigator's Brochure for more detailed information on clinical experience with ONTAK.

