4.1.2 Secondary Objective(s)

- To determine the duration of response (DOR) for E7777
- To determine time to response (TTR) after E7777 treatment
- To determine skin response after E7777 treatment
- To determine duration of skin response after E7777 treatment
- To determine time to skin response after E7777 treatment
- To assess ORR for E7777 using the alternate response assessment criteria of Prince (2010)²
- To evaluate safety and tolerability of E7777 in all subjects
- To evaluate safety and tolerability of E7777 in the Stage I – III Main Study subjects plus the Stage I – III Lead-In subjects from the 9 µg/kg/day dose group
- To characterize the pharmacokinetics (PK) of E7777 and immunogenicity after treatment with E7777

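### SAP 6.6.2 defines no treatment-induced or treatment-boosted antibody and no within-subject titre change, so boosting in subjects already positive at baseline cannot be identified

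*SAP*

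**What the plan says.** Immunogenicity is part of a secondary objective in SAP 4.1.2: "To characterize the pharmacokinetics (PK) of E7777 and immunogenicity after treatment with E7777".

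SAP 6.6.2 plans the following, on the Safety Analysis Set:
- Sampling: "A predose blood sample for immunogenicity assessment will be collected prior to dosing on Day 1 in Cycles 1, 2, 3, 5, and 8". The Cycle 1 sample is therefore a true baseline.
- Positivity: "Anti-E7777/IL-2 antibodies results (negative/positive) will be summarized by number of subjects and percentage by visit".
- Titres, for subjects with a positive result only: "antibodies, the titer levels will be summarized using descriptive statistics (n, mean (SD), Q1, Q3, median, minimum and maximum) by visit".
- Neutralising antibody results by visit, and one semi-log box plot of titres by cycle.

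Neither document defines a treatment-emergent, treatment-induced or treatment-boosted antibody. Neither plans a change or fold change in titre from baseline, a shift by baseline antibody status, or a geometric mean titre. Baseline titre appears only as the end point for long-term anti-IL-2 follow-up.

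Protocol 7.3.1 gives the background for the predecessor product: "At baseline, 66% of subjects (N=95) tested positive for antibodies to denileukin diftitox". Positivity on that product then climbed to 94%, 99% and 100% over the first three cycles. The section adds: "Antibody titers increased after 2 cycles, with PK parameters indicating decreased systemic exposure to drug".

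**The concern.** When most subjects are positive before the first dose, treatment can act on antibodies in two ways. It can turn negative subjects positive, or it can raise titres in subjects who are already positive. A percentage positive by visit responds only to the first. The second is the one that Protocol 7.3.1 reports alongside falling exposure on the predecessor.

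The titre summary could in principle show boosting, but it is restricted to subjects positive at each visit. At baseline that is the pre-existing positives. One cycle later it is those subjects plus the new converters. The two summaries describe different groups, so their difference is not a within-subject rise.

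At stake is how well a descriptive secondary objective is answered. Protocol 9.7.1.8 also plans to relate the presence of anti-E7777 antibodies to response and adverse events. If nearly everyone is positive on treatment, presence gives little contrast, whereas a boosted category or a fold rise could give one.

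**Working it through.** **Inputs from the documents (Protocol 7.3.1, predecessor product, antibodies to denileukin diftitox).** Baseline positivity b = 66% (N=95). Positivity p = 94%, 99% and 100% after 1, 2 and 3 cycles. In this trial's sampling plan, after one cycle is the Cycle 2 pre-dose sample and after two cycles is the Cycle 3 pre-dose sample. No sample falls exactly after three cycles. The documents give no titres and no baseline rate for E7777 or for anti-IL-2.

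**Step 1. Reproduce the stated rate.** 63/95 = 66.3%, exact 95% CI 55.9% to 75.7%. The stated 66% is reproduced.

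**Step 2. What percent positive can show.** The rise is p − b: 28 points after one cycle, 33 after two, 34 after three. Among baseline-negatives, the net conversion is at least (p − b)/(1 − b) = 0.28/0.34 = 82% after one cycle and 0.33/0.34 = 97% after two. So net seroconversion can be read, provided that dropout between visits is small. The 66% already positive contribute nothing to the rise: the table reads 66% then 94% with no boosting and with 10-fold boosting alike. Scaled to 70 subjects for illustration, 0.66 × 70 ≈ 46 can show a treatment effect only as boosting, and about 24 can show it as conversion.

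**Step 3. How far the set of positives changes.** With no seroreversion, the share of positives who are new converters is (p − b)/p:
- after one cycle: 0.28/0.94 = 30%
- after two: 0.33/0.99 = 33%
- after three: 0.34/1.00 = 34%

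Almost all of the change falls between baseline and Cycle 2. With b at the limits of its CI and p held at 94%, the 30% becomes (0.94 − 0.757)/0.94 = 19% or (0.94 − 0.559)/0.94 = 41%.

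**Step 4. Effect on the titre comparison.** Assumptions: F is the true fold rise in baseline-positives, and r is the converters' geometric mean titre relative to the baseline geometric mean. With w = b/p, the ratio of visit geometric means among positives is F^w × r^(1−w). After one cycle w = 0.66/0.94 = 0.702; after three cycles w = 0.66. The arithmetic-mean ratio, assuming equal log SD at both visits, is wF + (1 − w)r. For F = 10:

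| r | Geometric-mean ratio, after 1 / 3 cycles | Arithmetic-mean ratio, after 1 / 3 cycles |
|---|---|---|
| 0.1 | 2.5 / 2.1 | 7.1 / 6.6 |
| 1 | 5.0 / 4.6 | 7.3 / 6.9 |
| 10 | 10 / 10 | 10 / 10 |
| 30 | 13.9 / 14.5 | 16.0 / 16.8 |

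The comparison is right only if converters reach the same level as boosted subjects (r = F). It is too low if they stay below and too high if they rise above.

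**Step 5. The arithmetic mean.** For log-normal titres the arithmetic mean exceeds the geometric mean by exp(s²/2), where s is the SD of the natural log. That factor cancels in a visit-to-visit ratio if s is constant. It does not cancel if the spread grows: a log10 SD rising from 0.5 to 0.8 multiplies the arithmetic-mean ratio by a further exp[(ln 10)² × (0.64 − 0.25)/2] = 2.8.

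**The case against.** Four points can fairly be made for the plan.

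- A reader might infer that the planned tables cannot show treatment-emergent immunogenicity at all. The documents do not support that. Cycle 1 pre-dose is a reported visit, and Step 2 shows that net conversion can be read from the percentages. What is missing is subject-level classification, and boosting.
- A reader might infer that the plan understates boosting. That holds only if converters' titres stay below those of boosted subjects. The documents give no titres, and Step 4 shows that the bias can reverse.
- The plan is not a mean alone. The median, quartiles and a semi-log box plot resist a few extreme titres and would show a large group shift. After Cycle 2, seroconversion changes the set of positives little: at most 6 points, from 94% to 100%. These points stand, but none of these summaries pairs a subject with their own baseline, and the step from baseline to Cycle 2 is where the composition changes.
- The 66% belongs to another product and another assay target. Protocol 7.3.1 offers it as relevant: "Since E7777 and ONTAK have a common active moiety, clinical experience with ONTAK in T-cell lymphoma provides relevant background information". But Protocol 7.1 also says that E7777 is purer, with fewer aggregates and misfolded species. The figure is an assumption for anti-E7777, and it should not be carried over to anti-IL-2.

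It can also be said that exposure is measured directly by PK in Cycles 1, 3 and 5, that SAP 6.6.1 allows further PK analyses by antibody status, and that SAP section 10 leaves derivations to separate specifications. These reduce the consequence. They do not supply the definitions, and a boosting cut-off is most credible when set before the titres are seen.

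**Conclusion.** The gap is real but modest. SAP 6.6.2 has no baseline-referenced antibody measure. If baseline anti-E7777 positivity resembles the predecessor's 66%, boosting in about two-thirds of subjects cannot be identified from the planned tables. The baseline-to-Cycle 2 titre comparison would also mix in about 30% new converters (19% to 41% over the CI of the baseline rate), with bias of unknown direction.

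This rests on three assumptions: the predecessor's rates carry over to anti-E7777, seroreversion is negligible, and the titre values in the illustration are hypothetical. The absence of a within-subject measure does not depend on any of them; only its size does. For anti-IL-2 the size cannot be stated.

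The endpoint is descriptive and secondary, with no hypothesis test attached. The primary ORR analysis is unaffected. This is a worthwhile improvement rather than a flaw that threatens the trial's conclusion.

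**What to change.** In SAP 6.6.2, separately for anti-E7777 and anti-IL-2, add:

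1. A shift table by baseline antibody status. Treatment-induced antibody is negative at baseline and positive later, with baseline-negatives as denominator. Treatment-boosted antibody is positive at baseline with a titre rise of at least a stated multiple, with baseline-positives as denominator. Fix the multiple from assay precision before the analysis; 4-fold would be one example, but the documents give no basis for any particular value.
2. Geometric mean titre by visit, and paired within-subject fold change from baseline with a 95% CI, in subjects with a titre at both visits. Keep the planned median and quartiles alongside. If negatives are given an imputed titre (half the minimum reportable value, for example), report that as a sensitivity analysis, because the imputed value would drive the fold change in converters.

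The cost is two extra tables for each antibody and one cut-off to pre-specify. The scheduled pre-dose samples suffice. The SAP already plans change from baseline and shift tables for laboratory values (6.7.3) and geometric means for PK parameters (6.6.1), so the methods are not new to it.

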6.6.3 Pharmacodynamics, Pharmacogenomic, and Other Biomarker Analyses

Not applicable.

6.7 Safety Analyses

All safety analyses will be performed for the Safety Analysis Set and the Stage I-III Safety Analysis Set. Safety data will be summarized using descriptive statistics (eg, n, mean, standard deviation (SD), median, Q1, Q3, minimum and maximum for continuous variables; number and percentage for categorical variables). Safety data to be evaluated include adverse event (AEs), clinical laboratory results, vital signs, ECGs.

6.7.1 Extent of Exposure

The number of cycles/infusions on treatment, quantity of study drug administered, and duration of study drug treatment will be presented. The number of subjects requiring dose reductions, treatment interruption will be summarized.

- The number of cycles received and the number of infusions by cycle and overall will be summarized with descriptive statistics. Subject is considered to have received one cycle if the subject received at least one dose on any of days 1, 2, 3, 4 or 5 of a cycle during the cycle.
- The duration of study drug in weeks will be $(\text{Date of the last dose} - \text{Date of the first dose} + 1) / 7$, including drug interruption days.
- Total dose (ug/kg) of study drug is the summarization of all the actual doses received during study. Actual dose (ug/kg) is calculated using $\text{planned dose (ug/kg)} \times (\text{actual volume(ml)}/\text{planned volume(ml)})$.
- Received dose as percentage of planned starting dose (%) = $\text{total dose (ug/kg)} / (\text{number of cycles} \times 5 \text{ (day)} \times 9 \text{ (ug/kg/day)}) \times 100$.
- Number of subject weeks = summation over all subjects' exposure durations.

Subject data listings will be provided for all dosing records, and for the summary statistics calculated above.

Study drug interruption and dose reduction instructions for subjects who experience an E7777-related toxicity are presented in Table 1 per protocol amendment 6 section 9.4.1.5. The number of subjects with dose reductions and treatment interruption will be summarized by counts and percentages.

6.7.2 Adverse Events

Adverse events will be summarized for the Safety Analysis Set and Stage I-III Safety Analysis Set. Adverse events were graded using Common Terminology Criteria for Adverse Events (CTCAE) version 4.03 or version 5.0. CTCAE version was upgraded from 4.03 to 5.0 in Protocol Amendment 05 (03 May 2018). Investigators will collect all AE CTCAE grades (for both increasing and decreasing severity). AEs will be classified into standardized

medical terminology from the verbatim description using the Medical Dictionary for Regulatory Activities (MedDRA version 24.0 or most recent version). AEs will be summarized by preferred term (PT) nested within system organ class (SOC). All AEs will be listed.

A TEAE is defined as an AE that emerged during treatment or up to 30 days (also 30 days for serious TEAEs) following last dose of study drug; AEs that emerge during study drug treatment, having been absent at pretreatment (Baseline), or those that:

- Reemerge during study drug treatment, having been present at Baseline but stopped prior to study drug treatment, or
- Worsen in severity during study drug treatment relative to the pretreatment state, when the AE is continuous.

Only those AEs that are treatment emergent will be included in summary tables. All AEs, treatment emergent or otherwise, will be presented in subject data listings.

An overview table, including the incidence of and the number of subjects with treatment-emergent adverse events (TEAEs), SAEs, deaths, and those TEAEs that led to discontinuation from study drug, dose reduction or drug interruption, will be provided. The incidence of TEAEs will be summarized by SOC, PT, CTCAE grade, and relatedness to study drug (possibly related or probably related). Although a MedDRA term may be reported more than once for a subject, that subject will be counted only one time in the incidence count for that MedDRA term with the highest CTCAE grade (in the summary by CTCAE grade) or with the closest relationship to study treatment (in the summary by relatedness to study treatment). Treatment-related TEAEs includes TEAEs considered by the Investigator to be possibly or probably related to study drug or TEAEs with missing causality.

Separate summary tables and listings will be provided for all TEAEs, treatment-emergent SAEs, TEAEs reported as treatment-related, treatment-emergent SAEs reported as treatment-related, TEAEs by CTCAE grade, and TEAEs leading to treatment discontinuation.

In summary, the following TEAE tables will be provided:

- Overview of TEAEs
- Overview of treatment-related TEAEs
- TEAEs by SOC and PT and Worst CTCAE Grade
- TEAEs by PT in decreasing frequency
- Treatment-related TEAEs by SOC and PT and Worst CTCAE Grade
- Treatment-related TEAEs by PT in decreasing frequency
- Treatment-emergent serious TEAEs by SOC and PT
- Treatment-emergent serious TEAEs by PT in decreasing frequency
- Treatment-related serious TEAEs by SOC and PT
- Treatment-related serious TEAEs by PT in decreasing frequency
- TEAEs leading to discontinuation from study drug by SOC and PT

- TEAEs Leading to dose reduction or drug interruption by SOC and PT
- TEAEs leading to dose reduction by SOC and PT
- TEAEs leading to drug interruption by SOC and PT

The following listings of deaths and AEs will be prepared:

- All AEs
- Adverse events with CTCAE grade 3 or higher
- All Serious adverse events
- All deaths
- Adverse Events leading to study drug discontinuation
- Adverse Events leading to dose reduction or drug interruption

Note that for summary tables, if data are not adequate for summary, only listings will be provided.

6.7.2.1 Treatment-Emergent Adverse Events of Clinical Interest

TEAEs of special interest (AESI) for E7777 will be identified based on the review of safety data by Clinical and Pharmacovigilance.

AESI will be summarized by preferred terms and worst CTCAE grade.

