#### 9.1.2 Lead-In Part

A Continual Reassessment Method (CRM) will be employed to determine the MTD of E7777,

targeting a rate of dose-limiting toxicity (DLT) of approximately 20%.

Subjects will be treated with E7777 for 5 consecutive days during every cycle of 21 days. The doses of E7777 that may be used are 3, 6, 9, 12, 15, or 18 µg/kg/d, with 6 µg/kg/d specified as the starting dose. Each subject will be assigned a dose of E7777 in accordance with the rules of the CRM design. The CRM design is described under [Section 9.7 “Statistical Methods.”](#)

Dose-limiting toxicities are based on known toxicities of ONTAK, as described in the US product label. A DLT will be any of the following occurring within the **first cycle** of therapy:

- Serious infusion reaction, defined as CTCAE Grade 4 adverse event of “Infusion related reaction”, or recurrent CTCAE Grade 3 despite administration of systemic steroid premedication after initial occurrence. Infusion reactions are defined as symptoms (e.g., fatigue, nausea, vomiting, arthralgia, myalgia, pyrexia, chills, rigors) occurring within 24 hours of E7777 infusion.

- Capillary leak syndrome (CLS) CTCAE Grade 4 or Grade 3 (with exceptions).

The CTCAE definitions are broad and general, therefore the following guidance is provided:

- Grade 4 is life-threatening severity such as subjects experiencing hypovolemic shock or renal failure, or who need treatment with vasopressors or oxygen
- Grade 3 is severe symptoms (less severe than the Grade 4 symptoms above) that may or may not be dose-limiting. For example, severe symptoms requiring hospitalization for acute intervention would be a DLT, whereas less severe symptoms leading to hospitalization for prophylactic treatment with fluids or diuretics would not be a DLT. Hospitalization or medical intervention to prevent hospitalization is not in itself a DLT as the threshold for hospitalization may differ by doctor and region.

CLS is defined as the noted occurrence of at least 2 of the following: hypotension, edema, or serum albumin < 3.0 g/dL. These are not required to occur simultaneously to be characterized as CLS.

- Clinical visual impairment. This could be loss of visual acuity and/or color vision.
- Any CTCAE ≥ Grade 4 adverse event that may represent an infusion reaction.
- Any CTCAE Grade 3 adverse event that may represent an infusion reaction that prevents the entire dose of E7777 from being administered despite appropriate treatment.

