**Table 1 Dose Interruption and Modification During Treatment Period**

Toxicity	Dose Interruption	Dose Modification

CLS = capillary leak syndrome, CTCAE = Common Terminology Criteria for Adverse Events, IRR = infusion-related reaction, N/A = not applicable.
 
a Refer to Section 9.1.2 for definition of capillary leak syndrome (CLS) and of DLT for CLS
 
b Infusion reactions are infusion related reactions that occur within 24 hr of E7777 administration; see Section 9.1.2 definitions
 
c Infusion related reactions can occur at any time during the treatment cycle
 
d Visual loss is defined as visual acuity impairment, color or shape distortion, or blurred vision
 
e These toxicities were observed for E7777 in a Phase 1 study and are expected toxicities.
 
f See Section 9.4.1.1 for detailed instructions on systemic steroid premedication
		

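### SAP 6.7.2.1 does not name the adverse events of special interest or say how to count protocol-defined capillary leak syndrome, so the planned tables cannot give its incidence

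*SAP*

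**What the plan says.** SAP 6.7.2.1 has two sentences. The first says that AESI "will be identified based on the review of safety data by Clinical and Pharmacovigilance". The second is "AESI will be summarized by preferred terms and worst CTCAE grade". No event is named, and no term grouping or derivation is given. The SAP text mentions neither CLS nor infusion reaction as an event. In the general adverse event tables (SAP 6.7.2) the counting unit is the MedDRA term: "that subject will be counted only one time in the incidence count for that MedDRA term with the highest CTCAE grade".

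The protocol is more specific. Section 7.3.1 singles out infusion reaction and CLS in the experience with the predecessor product. Section 9.1.2 says: "CLS is defined as the noted occurrence of at least 2 of the following: hypotension, edema, or serum albumin < 3.0 g/dL". It adds: "These are not required to occur simultaneously to be characterized as CLS". Table 1, footnote a, refers back to that section, so the definition also applies to dose decisions during treatment. Footnotes b and c separate infusion reactions (within 24 hours of administration) from infusion related reactions (any time in the cycle). Sections 9.5.4.2 and 9.5.7.3 make vision loss an event of interest that goes through the SAE reporting route even when nonserious.

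**The concern.** The protocol defines CLS across two adverse event concepts and a laboratory value. A subject with hypotension and edema recorded as two adverse events meets that definition. So does a subject with one of them plus an albumin of 2.7 g/dL. Unless the investigator also recorded CLS, such a subject appears in separate rows and tables and adds nothing to the CLS row.

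This is a single-arm registrational study with safety as a secondary objective. With no comparator, absolute incidence is the safety result. A CLS incidence that depends on how each site names the event, and that cannot be set against the protocol's own definition, is a weak basis for describing a principal known harm. Nothing in the documents required the AESI list to stay open: the Lead-In study report was completed in January 2019 and this SAP is dated 25 February 2022.

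**Working it through.** The documents state no expected CLS rate, component rate or safety precision target, so there is no figure of the plan's to reproduce. The check has three steps.

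**1. What each planned display can say about CLS**

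| SAP display | What it counts | What it cannot show |
|---|---|---|
| 6.7.2, adverse event tables | subject once per MedDRA term | which subjects had both hypotension and edema |
| 6.7.2.1, AESI table | preferred terms by worst grade | component-only cases not labelled CLS |
| 6.7.3.1, grade summaries and shifts | albumin by CTCAE grade | any link to adverse events |
| 6.7.3.1, markedly abnormal values | values outside range with a rise of 2 or more grades | a one-grade worsening to below 3.0 g/dL |
| 6.7.4, vital signs | blood pressure by visit | any link to edema or albumin |

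The fourth row matters because Protocol 9.4.1.3 equates albumin below 3.0 g/dL with Grade 2 or more. A subject at Grade 1 at baseline who falls to Grade 2 has risen 2 − 1 = 1 grade and is not counted as markedly abnormal. Protocol 9.5.4.1 also exempts albumin from its automatic two-grade adverse event rule and leaves it to the investigator's judgement. Other criteria there, such as reaching Grade 2 on the sponsor's laboratory grading or withholding of study drug, can still make it an adverse event. A qualifying albumin therefore can, but need not, miss both tables. It would still appear in the shift table, unlinked to that subject's adverse events.

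**2. Can component totals recover the CLS count?**

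Let a ≥ b ≥ c be the numbers of subjects with each component, and N = 70 (the approximate Stage I–III target). Each subject who meets the rule uses at least two component counts, so the maximum is min(⌊(a + b + c)/2⌋, b + c). When a + b + c ≤ N the components can fall in different subjects, so the minimum is 0. All totals below are assumptions.

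| Assumed totals | Sum | Subjects with at least 2 of 3 |
|---|---|---|
| 7, 7, 7 | 21 | 0 to 10 (0–14%) |
| 14, 14, 14 | 42 | 0 to 21 (0–30%) |
| 21, 18, 14 | 53 | 0 to 26 (0–37%) |
| 21, 21, 21 | 63 | 0 to 31 (0–44%) |

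For 21, 18, 14: ⌊53/2⌋ = 26, b + c = 32, and 53 ≤ 70. An integer linear programme gave the same bounds in all four rows. Independence of the components is one point inside the range: with h, e, s the three proportions, he + hs + es − 2hes = 0.158, or 11.0 of 70. The component totals alone do not determine the CLS count.

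**3. What the CLS row shows if only a share of cases carries the label**

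Assume 14 of 70 truly meet the definition (20.0%; exact 95% CI 11.4–31.3%).

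| Assumed share labelled CLS | Subjects in row | Incidence (exact 95% CI) |
|---|---|---|
| 100% | 14 | 20.0% (11.4–31.3) |
| 75% | 10 (10.5 rounded) | 14.3% (7.1–24.7) |
| 50% | 7 | 10.0% (4.1–19.5) |
| 25% | 4 (3.5 rounded) | 5.7% (1.6–14.0) |

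The shortfall runs from none to (14 − 4)/14 = 71%. It is set entirely by the assumed share, about which the documents say nothing.

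**The case against.** The best defence is that sites will probably use the syndrome term. Table 1 has the investigator act on CLS by grade and points to the 9.1.2 definition. Section 9.4.1.3 calls for CPK testing when CLS is suspected. Section 9.5.4.1 says laboratory abnormalities that belong to a reported clinical syndrome should not be listed separately. Table shells and dataset specifications are separate documents that were not available and may hold term groupings. All adverse events are listed, albumin shifts are shown, and events leading to interruption, reduction or discontinuation are tabulated.

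Much of this stands, and it rules out several stronger readings that a reader might infer.

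- *CLS is undercounted.* The documents show that this can happen, not that it does or how often.
- *The AESI list is chosen after the results are known.* Section 6.7.2.1 does not say when the review takes place or which data it covers, and Lead-In safety data already existed. The fair statement is that the list is not pre-specified.
- *Each AESI is a single preferred term.* The SAP says preferred terms, in the plural. Grouping is not stated, but its absence from the shells is not established.
- *Infusion reactions are biased downward.* A row for infusion related reaction has no 24-hour limit and could overcount the 24-hour category. Chills or pyrexia coded separately would undercount it.
- *Every listed symptom within 24 hours is an infusion reaction.* Section 9.1.2 gives the symptoms as examples. With dosing on five consecutive days, such a rule would sweep in almost any untimed nausea or fatigue on Days 1 to 6.

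The defence does not supply a display that counts the protocol's composite. The listings hold the raw material, but a reader would have to build the count by hand.

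**Conclusion.** The point holds in a limited form. The SAP does not pre-specify AESI, and its stated tables cannot yield the incidence of CLS as the protocol defines it. The CLS row gives investigator-labelled CLS only. The gap between the two lies anywhere from none to large. The figures above are illustrations at N = 70 with assumed rates and are not estimates. For infusion reaction the possible misclassification has no fixed direction.

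An open AESI list alone would be only a missing detail. The point merits action because a derived count is cheap, uses data already collected and answers a question that the planned tables leave open. It rests on the SAP text as published; if the shells or specifications already contain such a derivation, it should be brought into 6.7.2.1.

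**What to change.** Before database lock, revise SAP 6.7.2.1 as follows.

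1. Name CLS, infusion reaction and vision loss as AESI. Later additions should be labelled as such. Keep the preferred-term table.
2. Add a derived-CLS row for the Safety Analysis Set and the Stage I–III Safety Analysis Set. A subject counts with at least two of: an adverse event of hypotension; an adverse event of edema (terms listed in advance for both); on-treatment albumin below 3.0 g/dL, from the central laboratory or its local substitute. As in the protocol, the components need not be simultaneous. A same-cycle window may be shown only as a labelled sensitivity count, because Section 9.1.2 contains none.
3. Show this beside investigator-reported CLS, with the worst grade of the contributing adverse events and exact 95% CIs. Sites may fold the components into one CLS event, so also give the number meeting either criterion.
4. For infusion reaction, split the events reported as infusion reaction or infusion related reaction by onset within 24 hours or later, matching Table 1 footnotes b and c. State a calendar-day convention for events without an onset time.
5. For vision, reconcile the wordings in the Synopsis (loss of visual acuity), Section 9.1.2 (clinical visual impairment) and Table 1, where "Visual loss is defined as visual acuity impairment, color or shape distortion, or blurred vision", before grouping terms.

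The cost is SAP wording and one derived dataset from adverse event, laboratory and dosing records. The either-criterion CLS count will equal or exceed the reported one and may include some unrelated component pairs, which the side-by-side display makes visible. No clinical rule changes.
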